There is no anticipated additional risk from a potential PK interaction for cohorts coadministered TAK-071 and donepezil. Indeed, currently available in vitro data indicate that the risk of PK interaction between these 2 compounds is low. From a PD interaction point of view, it is anticipated that these 2 compounds might have synergistic effects. For this reason, in the healthy subject combination treatment cohorts, there will be 3 TAK-071 dose escalation steps, after each of which there will be a review of the safety/tolerability and available PK data. Subjects with MCI or mild AD on stable donepezil will only be dosed after review of the safety/tolerability and available PK of the combination treatment cohorts in healthy subjects.

Overall, based on the substantial exposure safety margin for the initial clinical dose and all the available preclinical pharmacology, toxicology, drug metabolism, and PK data, TAK-071 alone or in combination with donepezil is not anticipated to present unacceptable risks to healthy (non-Japanese or Japanese) subjects or to subjects with MCI or mild AD at the proposed doses and dose regimens. This study is not designed to allow the assessment of the therapeutic potential for this compound, and it is not expected that this study will result in any therapeutic benefit for the included study populations. However, data generated from this study should enable the investigation of TAK-071 in subsequent clinical proof-of-mechanism (PoM) and efficacy studies of longer duration in the relevant subject populations (ie, phase 2).

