A dose of 5 mg QD has been selected for the healthy subject cohorts (10 to 12) because the target population of patients with AD is known to better tolerate cholinomimetic treatments as compared with healthy young adults [12]; thus, a dose of 5 mg is thought to be appropriate for the purposes of an initial evaluation of the safety, tolerability, and PK of the donepezil plus TAK-071 combination. Because PK sampling for donepezil plasma concentrations will be performed in these cohorts, for practical purposes and to avoid PK sampling overnight, donepezil dosing will occur in the morning simultaneously with TAK-071. This will also provide an opportunity to evaluate the potential for a drug-drug interaction of TAK-071 on donepezil while at steady-state. For this reason, the exact dosing time of donepezil relative to TAK-071 will be selected so as to ensure that both drugs attain their peak concentrations at approximately the same time to maximize the potential for interaction. Donepezil is reported to have a t_{max} of 3 to 4 hours, and preliminary TAK-071 PK data from SRD Cohorts 1 to 4 indicates that maximum, or near maximum, plasma concentrations are attained approximately 4 hours postdose; thus, donepezil should be dosed approximately 1 hour after TAK-071; however, the definitive dosing time of donepezil relative to TAK-071 will be confirmed following evaluation of all preliminary PK data from the SRD part of the FIH study.

According to the donepezil (Aricept) product label, the recommended starting dosage of donepezil is 5 mg administered once per day in the evening, just prior to retiring. The maximum recommended dosage in patients with mild-to-moderate AD is 10 mg per day. A dose of 10 mg should not be administered until patients have been on a daily dose of 5 mg for 4 to 6 weeks. Because the majority of patients with mild AD are prescribed donepezil 10 mg QD, 10 mg has been selected as the donepezil dose for Cohort 16. To minimize variability, subjects who are regularly taking this dose in the evening, as recommended in the product labeling [11], will be recruited into the study. This will also provide safety and tolerability data for the combination treatment in the intended target population under realistic dosing regimen conditions and will also provide data at a higher donepezil dose than that tested in the preceding healthy subject cohorts.

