9.1.6 Vital Sign Procedure

In subjects who are not undergoing CSF collection (Cohorts 2, 4 to 8, and 10 to 22), vital signs will include body temperature (oral), respiratory rate, and orthostatic blood pressure and pulse (bpm).

In subjects who have completed enrollment for Cohort 1 at the time of this amendment and in subjects who are undergoing CSF collection (Cohorts 3 and 9), vital signs include body temperature (oral), respiratory rate, supine blood pressure (resting more than 5 minutes), and pulse (bpm).

Vital signs should be collected daily, predose and upon morning rising on days during confinement. In addition, vital signs should be collected in Cohorts 3 and 9 at approximately 5 hour postdose on Day 1 and Day 8 (Cohort 9 only). Vital signs may be repeated. All measurements will be recorded on the source documents and in the eCRF.

When vital signs are scheduled at the same time as blood draws, the blood draw will take priority, and vital signs will be obtained within 0.5 hour before the scheduled blood draw.

For BA/FE Cohort 17, for the fed regimen, if vital signs coincide with a meal, vital signs will take precedence followed by the meal.

For Cohorts 2, 4 to 8, and 10 to 22, orthostatic blood pressure and pulse will be measured at predose and at 2, 4, 6, 8, and 12 hours postdose in the first 24 hours after the initial dose of TAK-071 (Day 1) and then afterwards on days while subjects are in the phase 1 unit. Orthostatic blood pressure will be measured as follows [23]:

1. Have the patient lie down for 5 minutes.
2. Measure blood pressure and pulse rate.
3. Have the patient stand.
4. Repeat blood pressure and pulse rate measurements after standing 1 and 3 minutes.

A drop in bp of ≥ 20 mm Hg, or in diastolic bp of ≥ 10 mm Hg, or experiencing lightheadedness or dizziness is considered abnormal [23].

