C-SSRS (q)	X	X					X		X	(X)
CCI										
Pupillometry (s)		X	X	X						

Footnotes are on the following page.

ET=Early Termination Visit, HBsAg=hepatitis B surface antigen, HCV=hepatitis C virus.

- (a) A PK blood sample should be collected at the Early Termination Visit, if possible.
- (b) Follow-up will occur by telephone on Day 12 (± 2) unless abnormal clinically significant findings are observed upon discharge. In these cases, subjects must then be brought back to the clinic for re-evaluation per investigator's discretion.
- (c) Vital signs (oral temperature, respiration, pulse, and blood pressure) will be obtained as indicated. In addition, orthostatic blood pressure will be measured at predose and at 2, 4, 6, 8, and 12 hours postdose in the first 24 hours after the initial dose of TAK-071 and then daily afterwards while subjects are confined in the phase 1 unit as detailed in Section 9.1.6.
- (d) Height and BMI will be collected at Screening only.
- (e) All ongoing medications will be recorded from Screening and throughout the study.
- (f) Blood and urine samples for clinical laboratory tests (hematology, coagulation, serum chemistry, urinalysis) will be collected as indicated. On Day 1, the urine sample for urinalysis will be taken predose (within 2 hours prior to dosing) and the blood sample will be taken 1 hour postdose. On subsequent days, blood and urine samples will be taken upon rising in the morning under fasted condition.
- (g) During the course of the study, regular serum hCG pregnancy tests will be performed for female subjects and subjects will receive continued guidance with respect to the avoidance of pregnancy as part of the study procedures. In addition to a negative serum hCG pregnancy test at Screening, female subjects must have a negative serum hCG pregnancy test at Check-in prior to receiving the first dose of study drug.
- (h) FSH concentration will be obtained from postmenopausal women (defined as continuous amenorrhea of at least 2 years and not surgically sterile).
- (i) A standard 12-lead ECG will be recorded at Screening, Check-in (Day -1), Day 1 (predose [within 60 minutes prior to dosing], and at 0.5, 1, 2, 4, and 8 hours postdose), and Days 2 through 5 (upon morning rising) or ET. Single ECGs will be taken at all visits.
- (j) Blood samples for PGx analysis will be collected as follows: 6 mL for DNA on Day 1; 2 \times 2.5 mL for RNA analysis on Day 1 (predose and 12 hours postdose) and Day 5.

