- (k) TAK-071 as DIC will be dispensed for treatment. Donepezil 10 mg will be administered approximately 24 hours after TAK-071 dose.
- (l) Blood samples for TAK-071 PK (up to 3 mL/sample collected into K₂EDTA-coated tubes) for plasma measurement of TAK-071 will be collected predose (within 30 minutes prior to dosing) and at specified time points outlined in Section 9.1.15.
- (m) Blood samples for donepezil PK (up to 4 mL/sample collected into sodium heparin tubes) for plasma measurement of donepezil will be collected predose (within 30 minutes prior to dosing) and at specified time points outlined in Section 9.1.15.
- (n) PTEs will be collected from signing of informed consent up until dosing on Day 1.
- (o) Any event after dosing on Day 1 will be captured as an AE.
- (p) Bowel function will be assessed using the BSF scale and daily stool count.
- (q) C-SSRS will be determined as indicated. If clinically significant at Final Visit, C-SSRS will also be determined as part of the Follow-up Visit.
- (r) ^{CCI}
^{CCI}
- (s) Pupillometry will be performed at check-in on Day -1 (approximately 25 hours predose), Day 1 (1 hour predose), and Day 2 (approximately 23 hours post TAK-071 dose) and 5 hours post donepezil dose.

ET=Early Termination Visit, HBsAg=hepatitis B surface antigen, HCV=hepatitis C virus.

(a) A PK blood sample should be collected at the Early Termination Visit if possible.

(b) Follow-up will occur by telephone on Day 32 (± 2) unless abnormal clinically significant findings are observed upon discharge. In these cases, subjects must then be brought back to the clinic for re-evaluation per investigator's discretion.

(c) Vital signs (oral temperature, respiration, pulse, and blood pressure) will be obtained as indicated. In addition, orthostatic blood pressure will be measured at predose and at 2, 4, 6, 8, and 12 hours postdose in the first 24 hours after the initial dose of TAK-071 and then daily afterwards while subjects are confined in the phase 1 unit as detailed in Section 9.1.6.

(d) Height and BMI will be collected at Screening only.

(e) All ongoing medications will be recorded from Screening and throughout the study.

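### In Cohorts 20 to 22 the serial ECG and orthostatic readings follow the Day 1 TAK-071 dose only, so scheduled readings miss the donepezil peak and roughly the first 22 hours of combined exposure

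*Protocol*

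**What the plan says.** In Cohorts 20 to 22, six subjects per cohort receive TAK-071 then donepezil, three receive donepezil with TAK-071 placebo, and three receive placebo for both. Appendix A footnote (k) gives the order: "Donepezil 10 mg will be administered approximately 24 hours after TAK-071 dose".

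The ECG schedule is in footnote (i) of the same table. After the Day 1 predose reading it runs "and at 0.5, 1, 2, 4, and 8 hours postdose), and Days 2 through 5 (upon morning rising". The recordings are not replicated: "Single ECGs will be taken at all visits". Table 9.b lists no Holter monitoring for these cohorts.

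The orthostatic schedule is in footnote (c). Its serial readings are at predose, 2, 4, 6, 8 and 12 h. The footnote ties them to TAK-071: "hours postdose in the first 24 hours after the initial dose of TAK-071 and then daily afterwards while subjects are confined in the phase 1". It gives no clock time for the daily reading. The general rule in Section 9.1.6 does: "Vital signs should be collected daily, predose and upon morning rising on days during confinement". SAP Sections 7.12.3 and 7.12.4 carry the same ECG and orthostatic times for the SRD cohorts and add nothing after donepezil.

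Other Day 2 procedures are timed to donepezil. Table 9.i draws donepezil PK at 1, 2, 3, 4, 6, 8, 12 and 16 hours after that dose and TAK-071 PK hourly from 24 to 28 hours. Appendix A footnote (s) places pupillometry 5 hours after donepezil.

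**The concern.** The fourth primary objective (Section 5.1.1) is to characterise a single 10 mg donepezil dose and compare it with the combination. Section 6.1 names ECG findings and vital signs among the means of assessing the combination in these cohorts, and says the cohorts will identify a well-tolerated combination dose for the next study. Section 4.3 expects a possible interaction: "From a PD interaction point of view, it is anticipated that these 2 compounds might have synergistic effects". The primary safety endpoints in Section 5.2.1.1 count subjects who meet the markedly abnormal value (MAV) criteria for ECG or vital signs at least once after dosing.

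The dense readings, however, are taken before anyone has received donepezil. At that stage the donepezil-alone and double-placebo arms have had identical treatment, so those readings say nothing about donepezil or the interaction. An MAV table without events could then be read as evidence of tolerability at peak combined exposure, although no scheduled ECG was taken there.

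**Working it through.** No power or sample-size figure is involved; Section 13.3 says the SRD part was not sized on power. The check is a timeline in hours after TAK-071.

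**Inputs**
- Donepezil dose: about 24 h (Appendix A, footnote (k)), fasted, with breakfast about 1.5 h later (Section 7.4.1), so it is a morning dose.
- Donepezil time to peak: 3 to 4 h; half-life above 70 h (both Section 6.2.2.4).
- Assumption: rising is 0 to 2 h before the clock time of dosing.

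**Position of the readings**
- Donepezil peak: 24 + 3 = 27 h to 24 + 4 = 28 h.
- Day 2 ECG on rising: 22 to 24 h, before donepezil.
- Next ECG, Day 3 on rising: 46 to 48 h. That is 46 − 24 = 22 h to 48 − 24 = 24 h after donepezil, and 46 − 28 = 18 h to 48 − 27 = 21 h after its peak.

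**Counts**

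| Quantity | Count |
|---|---|
| Scheduled ECGs after TAK-071, Days 1 to 5 | 5 (Day 1) + 4 (mornings, Days 2 to 5) = 9 |
| Before donepezil | 5 + 1 (Day 2 morning) = 6 |
| After donepezil | 3 (Days 3, 4, 5) |
| ECGs after 24 h and up to 36 h | 0 |
| Orthostatic readings after 24 h and up to 36 h, daily reading on rising | 0 |
| The same, daily reading at an unspecified time | at most 1 |
| Donepezil PK samples in the first 16 h after donepezil | 8 |
| TAK-071 PK samples after 24 h and up to 36 h | 7 |

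As a check that the PK schedule was read correctly, 21 TAK-071 samples × 3 mL = 63 mL and 15 donepezil samples × 4 mL = 60 mL, both as in Table 9.w.

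**Exposure at the Day 3 reading**

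Assuming mono-exponential decline from the donepezil peak, the fraction remaining after t hours is exp(−ln 2 × t / half-life).
- Donepezil, half-life 70 h: 0.837 at t = 18 h and 0.812 at t = 21 h, so about 81 to 84% of peak.
- TAK-071, relative to its level at the donepezil peak, using the 65 h and 140 h half-life thresholds in Section 6.2.2.2 as a range: 0.825 and 0.799 at 65 h, 0.915 and 0.901 at 140 h, so about 80 to 92%.

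A donepezil half-life above 70 h would raise its figure. A distribution phase after the peak would lower it.

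**Subjects affected**

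3 cohorts × (6 combination + 3 donepezil alone) = 18 + 9 = 27.

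**The case against.** The strongest reply is that the combination is not left unmeasured. The Day 3 to 5 readings are taken with both drugs present at a large fraction of their levels at the donepezil peak. SAP Sections 7.12.3 and 7.12.4 count unscheduled readings in the MAV summaries, Section 9.1.6 allows vital signs to be repeated, and adverse events are collected throughout Day 2. A reader might infer that the plan has no ECG or vital-sign data on the combination, or that a transient change would surface only as a symptomatic event. The documents support neither.

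The orthostatic gap is also less certain than the ECG gap. Footnote (c) says only daily, whereas the parallel footnotes for Cohorts 13 to 15 and Cohort 16 specify morning rising (or, for Cohort 16, arrival for an outpatient visit). The morning timing here is borrowed from the general sentence in Section 9.1.6.

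A reader might go further and name a specific harm, such as bradycardia or orthostatic hypotension at the donepezil peak. The documents do not identify one. The effects anticipated in Section 4.3 are gastrointestinal, and Section 6.2.2.4 describes single 10 mg donepezil doses as well tolerated in healthy subjects.

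Other cohorts do have serial ECGs on the combination: Cohorts 10 to 12 on Day 1 at steady-state donepezil, and Cohort 16 on four dosing days. This helps only in part. Cohorts 10 to 12 use 5 mg donepezil, and Cohort 16 takes 10 mg in the evening. Cohorts 18 and 19 have 48-hour Holter monitoring but no donepezil.

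Finally, Section 9.1 lets safety assessments be moved closer to peak concentrations, and protocol and SAP agree with each other. The first makes a correction easy but schedules nothing. The second means that the conflict lies between the schedule and the stated purpose of these cohorts, not between the two documents.

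**Conclusion.** The point holds in a limited form. No ECG is scheduled from the Day 2 donepezil dose until about 22 to 24 hours later, which leaves out the donepezil peak at 3 to 4 hours. The same is true of orthostatic readings if the daily reading is taken on rising; otherwise there is at most one, not linked to the donepezil dose. Six of the nine scheduled post-TAK-071 ECGs precede donepezil. What is missed is the peak and roughly the first 22 hours, in 27 subjects. Later combined exposure is covered.

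The ECG finding rests only on rising coming no more than about two hours before the clock time of dosing. The 81 to 84% figure also needs the 70-hour half-life and mono-exponential decline. This should be fixed because it weakens the ECG and vital-sign part of a primary comparison. It is not a fatal defect: the study is descriptive, later readings exist, and the documents name no specific cardiovascular risk at the peak.

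**What to change.** The sponsor should reconcile Appendix A footnotes (c) and (i) for Cohorts 20 to 22, Section 9.1.6, and SAP Sections 7.12.3 and 7.12.4 with the fourth primary objective and the stated purpose in Section 6.1. That means scheduling ECG and orthostatic readings relative to the Day 2 donepezil or placebo dose, at existing PK times that cover the donepezil peak. They can be added, or moved from the Day 1 series; the exact times are for the sponsor to choose. Footnote (c) should also state when the daily reading is taken. The SAP should summarise the new readings by time since donepezil.

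This applies to cohorts not yet dosed and to any further donepezil cohort that Section 6.1 allows. The documents do not show which of Cohorts 20 to 22 were already complete. For completed cohorts, the SAP should state that scheduled ECG and vital-sign MAV data on the combination begin about 22 hours after donepezil and do not describe the peak.

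The cost is a few extra or moved readings per subject on a day when subjects are confined and already being sampled, plus the wording changes. One row of the Cohorts 20 to 22 schedule is redacted, so the sponsor must check for clashes with that procedure and with the 5-hour pupillometry.

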Appendix B Responsibilities of the Investigator

Clinical research studies sponsored by the sponsor are subject to ICH GCP and all the applicable local laws and regulations. The responsibilities imposed on investigators by the FDA are summarized in the “Statement of Investigator” (Form FDA 1572), which must be completed and signed before the investigator may participate in this study.

The investigator agrees to assume the following responsibilities by signing a Form FDA 1572:

1. Conduct the study in accordance with the protocol.
2. Personally conduct or supervise the staff who will assist in the protocol.
3. Ensure that study related procedures, including study specific (nonroutine/nonstandard panel) screening assessments are NOT performed on potential subjects, prior to the receipt of written approval from relevant governing bodies/authorities.
4. Ensure that all colleagues and employees assisting in the conduct of the study are informed of these obligations.
5. Secure prior approval of the study and any changes by an appropriate IRB that conform to 21 Code of Federal Regulations (CFR) Part 56, ICH, and local regulatory requirements.
6. Ensure that the IRB will be responsible for initial review, continuing review, and approval of the protocol. Promptly report to the IRB all changes in research activity and all anticipated risks to subjects. Make at least yearly reports on the progress of the study to the IRB, and issue a final report within 3 months of study completion.
7. Ensure that requirements for informed consent, as outlined in 21 CFR Part 50, ICH and local regulations, are met.
8. Obtain valid informed consent from each subject who participates in the study, and document the date of consent in the subject’s medical chart. Valid informed consent is the most current version approved by the IRB. Each informed consent form should contain a subject authorization section that describes the uses and disclosures of a subject’s personal information (including personal health information) that will take place in connection with the study. If an informed consent form does not include such a subject authorization, then the investigator must obtain a separate subject authorization form from each subject or the subject’s legally acceptable representative.
9. Prepare and maintain adequate case histories of all persons entered into the study, including eCRFs, hospital records, laboratory results, etc., and maintain these data for a minimum of 2 years following notification by the sponsor that all investigations have been discontinued or that the regulatory authority has approved the marketing application. The investigator should contact and receive written approval from the sponsor before disposing of any such documents.
10. Allow possible inspection and copying by the regulatory authority of GCP-specified essential documents.

11. Maintain current records of the receipt, administration, and disposition of sponsor-supplied drugs, and return all unused sponsor-supplied drugs to the sponsor.
12. Report adverse reactions to the sponsor promptly. In the event of an SAE, notify the sponsor within 24 hours.

Appendix C Elements of the Subject Informed Consent

In seeking informed consent, the following information shall be provided to each subject:

1. A statement that the study involves research.
2. An explanation of the purposes of the research.
3. The expected duration of the subject's participation.
4. A description of the procedures to be followed, including invasive procedures.
5. The identification of any procedures that is experimental.
6. The estimated number of subjects involved in the study.
7. A description of the subject's responsibilities.
8. A description of the conduct of the study.
9. A statement describing the treatment(s) and the probability for random assignment to each treatment.
10. A description of the possible side effects of the treatment that the subject may receive.
11. A description of any reasonably foreseeable risks or discomforts to the subject and, when applicable, to an embryo, fetus, or nursing infant.
12. A description of any benefits to the subject or to others that reasonably may be expected from the research. When there is no intended clinical benefit to the subject, the subject should be made aware of this.
13. Disclosures of appropriate alternative procedures or courses of treatment, if any, that might be advantageous to the subject and their important potential risks and benefits.
14. A statement describing the extent to which confidentiality of records identifying the subject will be maintained, and a note of the possibility that regulatory agencies, auditor(s), IRB, and the monitor may inspect the records. By signing a written informed consent form, the subject or the subject's legally acceptable representative is authorizing such access.
15. For research involving more than minimal risk, an explanation as to whether any compensation and an explanation as to whether any medical treatments are available if injury occurs and, if so, what they consist of or where further information may be obtained.
16. The anticipated prorated payment(s), if any, to the subject for participating in the study.
17. The anticipated expenses, if any, to the subject for participating in the study.
18. An explanation of whom to contact for answers to pertinent questions about the research (investigator), subject's rights, and IRB and whom to contact in the event of a research-related injury to the subject.
19. A statement that participation is voluntary, that refusal to participate will involve no penalty or loss of benefits to which the subject otherwise is entitled, and that the subject may discontinue

participation at any time without penalty or loss of benefits to which the subject is otherwise entitled.

20. The consequences of a subject's decision to withdraw from the research and procedures for orderly termination of participation by the subject.
21. A statement that the subject or the subject's legally acceptable representative will be informed in a timely manner if information becomes available that may be relevant to the subject's willingness to continue participation in the study.
22. A statement that results of PGx analysis will not be disclosed to an individual, unless prevailing laws require the sponsor to do so.
23. The foreseeable circumstances or reasons under which the subject's participation in the study may be terminated.
24. A written subject authorization (either contained within the informed consent form or provided as a separate document) describing to the subject the contemplated and permissible uses and disclosures of the subject's personal information (including personal health information) for purposes of conducting the study. The subject authorization must contain the following statements regarding the uses and disclosures of the subject's personal information:
 - a) that personal information (including personal health information) may be processed by or transferred to other parties in other countries for clinical research and safety reporting purposes, including, without limitation, to the following: (1) Takeda, its affiliates, and licensing partners; (2) business partners assisting Takeda, its affiliates, and licensing partners; (3) regulatory agencies and other health authorities; and (4) IRBs;
 - b) it is possible that personal information (including personal health information) may be processed and transferred to countries that do not have data protection laws that offer subjects the same level of protection as the data protection laws within this country; however, Takeda will make every effort to keep your personal information confidential, and your name will not be disclosed outside the clinic unless required by law;
 - c) that personal information (including personal health information) may be added to Takeda's research databases for purposes of developing a better understanding of the safety and effectiveness of the study drug(s), studying other therapies for patients, developing a better understanding of disease, and improving the efficiency of future clinical studies;
 - d) that subjects agree not to restrict the use and disclosure of their personal information (including personal health information) upon withdrawal from the study to the extent that the restricted use or disclosure of such information may impact the scientific integrity of the research; and
 - e) that the subject's identity will remain confidential in the event that study results are published.
25. All female subjects must be of non-childbearing potential.

26. Male subjects must use adequate contraception (as defined in the informed consent) from Screening, throughout the duration of the study, and for 30 days after the last dose of study drug. If the partner or wife of the subject is found to be pregnant during the study, the investigator will offer the subject the choice to receive unblinded treatment information.
27. A statement that clinical trial information from this trial will be publicly disclosed in a publicly accessible website, such as ClinicalTrials.gov.

